the effects of VLNC are influenced by the concurrent availability of e-cigs varying in **nicotine concentration and flavors**. These procedures involve a sampling phase, in which the participant samples and rates the two options, followed by choice (preference) phase, consisting of a series of discrete trials in which the participant can choose between the two options (or choose to forgo either option). The option that is chosen more often is considered to have greater relative reinforcing efficacy (Comer et al., 2008). In addition to having strong internal and predictive validity (Carter et al., 2009), choice procedures have ecological validity as they mimic situations in which smokers choose which product to buy or use among those concurrently available in the natural environment. We considered a free-access procedure in which both options are made concurrently available and *ad libitum* consumption is measured, however choice procedures are generally more sensitive than free access procedures to differences among reinforcers (e.g., Griffiths et al., 1986; Shahan et al., 1999). Participants will complete **six sessions**, including the **Screening/Baseline (BL)** session, during which eligibility will be confirmed and background questionnaires will be completed. Participants will then complete five lab sessions, a minimum of 48 hours apart; each session will follow overnight smoking abstinence.

In **Lab Session 1**, only combusted cigarettes (either NNC or VLNC) will be available. This session will always occur first because, conceptually, the no-e-cig session is the baseline condition in this study; scheduling this session first ensures that smoking choices in this condition will not be affected by any potential carryover effects of e-cig exposure on smoking choices. During the sampling phase of the choice procedure ("Preference Task"), participants will sample and then rate the cigarette using the Product Rating forms. In the preference phase, participants will be prompted via computerized instructions to make a series of 10 choices. Each choice will be to either take 2 cigarette puffs or to abstain from puffing; a total of 20 cigarette puffs is available. After completing the choice task, participants will practice using the vaping devices and sample the e-liquid flavors available. They will select which cigarette and non-cigarette flavored e-liquids they want to use during Sessions 2-5.

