- 2) **Spot urine sample for smoking biomarker assessment:** Participants will be asked to provide a urine sample while in the lab to assess baseline total nicotine equivalents (TNEs). Samples will be stored at temperatures no more than -20°C. Urine samples will be sent regularly to be analyzed and stored at the University of Minnesota.

Researchers will complete the End of Visit Evaluation Form, which will be entered into REDCap.

Lab Session 1 Procedures

Participants will return for Lab Session 1 approximately one week after their screening visit. Session 1 scheduling window is a minimum of three days and maximum of 21 days later. Outside of this window, study staff should seek approval from the PI or Project Coordinator. Participants will arrive at each session having abstained from smoking sufficiently to achieve a breath CO level that is \leq 5 ppm or \leq 50% below the CO level obtained at screening/baseline.

During the Lab Session 1, participants (N=120) will be randomized equally into one of two experimental conditions (VLNC or NNC cigarettes). Participants will be assigned a cigarette that matches their menthol preference.

Physiological measures collected, recorded on paper, and entered into REDCap by the interviewer at the end of the visit:

- 1) CO (must be \leq 5 ppm or \leq 50% below the CO level obtained at screening/baseline to begin session)
- 2) Blood Pressure
- 3) Heart Rate
- 4) Urinary pregnancy test, if applicable

The following assessments will be administered as an interview and entered into REDCap by the interviewer:

- 1) Concomitant Medications Form
- 2) Health Changes Questionnaire, which will assess any health changes since the previous session
- 3) Adverse Event Form, if applicable, will assess the nature, severity, duration, action taken, and outcome of an adverse event.
- 4) TLFB Questionnaire

PRE-TASK assessments will be administered using Qualtrics or REDCap:

- 1) MNWS
- 2) QSU-10 Usual Brand Version
- 3) PANAS

Sampling Phase Procedures

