After a participant has completed all study procedures and has been paid for participation the research assistant should read the following script and give the participant the *CDC Tobacco Facts Sheet* and *Kick the Habit Manual*.

“Before you go, we want to encourage you to quit smoking cigarettes and stop using vaping devices. Quitting use of all tobacco products, including vaping devices, is best for your health. The risks associated with vaping devices are largely unknown. However, most public health experts agree that use of a vaping device instead of combustible cigarettes likely results in reduced health risks. We would like to provide you with some resources should you decide to try to abstain from smoking (give “Kick the Habit” and hotline information), and some online resources about vaping device risk (give list of online e-cigarette risk websites). Please also feel free to consult with your physician and use any medications he/she deems appropriate.”

The following assessment will be administered as an interview:

- 1) **Predicted Behavior Interview**, will assess hypothetical actions adolescents and/or adults may engage in to obtain conventional cigarettes in the event a low nicotine product standard for cigarettes is implemented.

The following assessment will be administered using Qualtrics or REDCap:

- 1) End of Study Questionnaire

Researchers will complete the End of Visit Evaluation Form, which will be entered into REDCap.

Debrief Information

If a participant withdraws before data collection and the final session are complete, researchers will attempt to speak with the participant to encourage them to quit smoking cigarettes and to stop using vaping devices. If unable to speak with the participant directly, we will mail debriefing information to the address on file.

30 Day Follow-Up Phone Call

Participants will receive a follow up phone call between 25 and 35 days after Lab Session 5 to assess their smoking patterns and tobacco product use since the study ended. If participants indicate increases in tobacco product use, then information on the potential harms will be reviewed and followed with a strong recommendation to quit using all tobacco products. Smoking cessation resources and referrals will be provided.

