Additionally, any Adverse Event Forms that remain open from the last session will be discussed. If the participant became pregnant during the study, this would have been recorded as an adverse event. During this visit, the research assistant will confirm her due date. This event will remain open until delivery. At that time the licensed medical professional will contact the participant to ask a few questions about the baby's health and will update the Adverse Event Form.

Follow-Up Qualitative Interview

A follow-up qualitative interview will be conducted remotely via Zoom or telephone with participants that previously completed the CENIC-2, P3 study, prior to the COVID-19 shutdown, and who agreed to be re-contacted with future research opportunities. This interview should take between 20-30 minutes and will be audio-recorded. After completion of the interview, participants will be sent via email a \$25 Amazon e-gift card for their time and participation. Participants will be provided the link to the Coping with Stress CDC website, <https://www.cdc.gov/coronavirus/2019-ncov/daily-life-coping/managing-stress-anxiety.html>.

In the case of minors who are interested in participation, research staff will call the minor's parent/guardian either by telephone or Zoom. The study information will be provided and any questions that the parent/guardian has will be answered by research staff. If the parent/guardian is willing to consent to their child's participation, the research assistant will complete the verbal consent process with the parent/guardian. If the parent/guardian is unable to complete the consent process at the time, staff may offer to email a copy of the consent form addendum to the parent/guardian and the verbal consent process will be scheduled at a later time. Minor participants will only be scheduled for an interview following verbal consent of their parent/guardian. Minor participants will provide verbal assent to participate. Participants and/or parents can request an emailed copy of the consent/assent form addendum to be saved or printed for their records.

Tobacco Product Information

Spectrum Cigarettes to be used in this project

Condition	TPMF Code	Type*	Specifications Nicotine Yield	Specifications Tar Yield	Specification Range for Nicotine Yield
NNC	NRC600	CN	0.8 ± 0.15	9 ± 1.5	0.65 - 0.95
NNC	NRC601	CN-Men	0.8 ± 0.15	9 ± 1.5	0.65 - 0.95
VLNC	NRC102	RN	0.03 ± 0.01	9 ± 1.5	0.02 - 0.04
VLNC	NRC103	RN-Men	0.03 ± 0.01	9 ± 1.5	0.02 - 0.04

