Participants are free to discontinue at any time and will receive compensation for the sessions completed at the same rate listed below. They will receive payment on the date when they would have completed the study. However, they will not receive the fixed bonus for attending all sessions. Study compensation will be administered to participants using the ClinCard payment system utilized by Brown University.

Screening- Eligibility Only	\$ 35.00
Baseline	\$ 35.00
Sessions 01-05	\$ 375.00
Completion Bonus	\$ 125.00
Total	\$ 570.00

Quit Attempts During the Study

At each lab session, we will assess cigarette smoking use via the TLFB. If the participant does not report

smoking any cigarettes on the TLFB, then the research assistant will ask the participant if she/he is currently abstaining with the intention of quitting for good.

If a Participant is Currently Abstaining from Smoking with the Intention to Quit:

- Encourage participant to continue abstaining from smoking
- Provide the participant with the 'Kick the Habit' manual and local smoking cessation resources
- Pay participant for visit attendance and end the visit.
- Participant will be withdrawn from the study.

Adverse Events and Withdrawal or Monitoring of Participants

Identifying Adverse Events

While participating in the study, adverse events and concomitant medications will be assessed at every study visit and vital signs and carbon monoxide will be obtained. Adverse events will typically be identified during the administration of the Health Changes Questionnaire. Other events may be identified from physiological study measures or by spontaneous reports during non-scheduled assessments.

Questionnaire items that will be reviewed:

- 1) *Have you had any negative changes in your physical or mental health since your last visit? If yes, briefly describe.*
- 2) *Since your last visit, have you received any form of medical care? If yes, briefly describe.*

No new AE required if one or more conditions below are met and the description does not otherwise meet the definition of an AE.

- a. Existing AE already open for reported symptom
- b. Pre-existing condition without increase in severity or frequency of symptoms (brief medical history will be updated if not previously reported).
- c. Received preventative or follow-up medical care.
- d. Other (explain).

Physiological data that will be reviewed:

- CO level: The 'Adverse Event Form' should be completed if the average CO within a visit is:

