3.2. Sample Size

Very little has been reported in the literature on the effect of VLNC cigarettes or the dual use of e-cigarettes on adolescent smokers. To determine a reasonable effect size (ES=mean diff/common SD) for sample size calculations, we considered several recent studies investigating alternatives to usual brand cigarettes in adolescents and young adults. In the first project of the CENIC 1 center grant, cigarettes per day (CPD) at weeks 2 and 6 were recorded for adult smokers using cigarettes with the same level of nicotine planned for our current project (15.8 mg/g vs 0.4 mg/g). (Donny et al., 2015) Selecting out the youngest participants (18-24 years of age), the comparison between these two nicotine groups resulted in an ES of 0.76 at 2 weeks and 0.85 at 6 weeks. A recent study of adolescent smokers (Cassidy et al., 2015) used a very similar design as the current proposal. Participants made a series of 20 choices between puffs of their usual brand cigarettes or money, where the amount of money varied over three sessions assigned to each subject in random order (\$0.00, \$0.10, \$0.50). The ES for the comparison between 10 and 50 cents was 0.73. Therefore, based on these previous studies, we determined that 60 subjects per cigarette group would allow for the detection of an ES of 0.60 or higher with minimum statistical power of 90% for a two-sided, two-sample test where the significance level is 0.05. For the within subject comparisons defined by the 2 factors for the e-cig characteristics, an ES of 0.5 or more for the two main effects would have at least 97% power in a repeated measures analysis if the sample size is 60 per cigarette group with a significance level of 0.05. Study enrollment will continue until the number of subjects completing all 5 sessions reaches 60 in each group (120 total). Sample size and power calculations were carried out using PASS 13 (NCSS, LLC. Kaysville, Utah, 2014).

4. Study Populations

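### No scheduled question about new adverse events follows product use in the last lab session, and the 30-day call is written to review only forms already open

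*Combined protocol and SAP*

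**What the plan says.** Under Identifying Adverse Events, the protocol states that during participation "adverse events and concomitant medications will be assessed at every study visit", and that "Adverse events will typically be identified during the administration of the Health Changes Questionnaire". The first item on that questionnaire is "Have you had any negative changes in your physical or mental health since your last visit"; the second asks about medical care received over the same period. Lab Session 1 Procedures describes the instrument as the "Health Changes Questionnaire, which will assess any health changes since the previous session". In Sessions 1 to 5 it is listed with the opening interview, ahead of the pre-task scales and the sampling phase.

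After product use in Session 5, the listed steps are a CO reading, the Predicted Behavior Interview, the End of Study Questionnaire and the staff evaluation form. None is described as asking about health changes.

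The 30-day call takes place 25 to 35 days after Session 5. Its stated purpose is "to assess their smoking patterns and tobacco product use since the study ended". On adverse events it adds that "any Adverse Event Forms that remain open from the last session will be discussed", and that a due date is confirmed if a participant became pregnant. Management of SAEs and Other Study Risks likewise has open events reviewed and closed at this contact. The Summary of Measures table marks adverse events at Lab Sessions 1 to 5 and has no column for the call.

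SAP 6.6 tabulates events by cigarette group, expects them to be extremely rare, refers to an Adverse Event SOP for recording, and plans no formal comparison.

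**The concern.** A backward-looking question asked before product use covers the previous session, not the current one. That works while another session is to come. After Session 5 the chain ends, and the one later contact is described as dealing only with tobacco use, forms already open and pregnancy follow-up.

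At stake is how completely safety is ascertained in participants aged 15 to 20 who have used study cigarettes and nicotine e-liquid. The protocol's risk section tells vaping users to watch for fever, fatigue and weight loss among other symptoms, and some of these would not show within a lab session. The item on medical care received is also a natural route to learning of a hospitalization, and serious-event reporting depends on someone learning of it. Where few events are expected, a few missed ones could change the table visibly.

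**Working it through.** The plan gives no figure for this point, so there is none to reproduce. The check is a count of sessions followed by a later scheduled health-change question.

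**Inputs**
- Lab sessions per participant: 5 (protocol, Overall Study Design: "Participants will then complete five lab sessions, a minimum of 48 hours apart").
- Sessions with e-cigarettes: 4 (Sessions 2 to 5).
- Planned completers: 60 per group, 120 in all (SAP 3.2).
- Puffs: 4 sampling puffs per product, and at most 20 in the preference phase.

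**Which sessions are covered**

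| Product use in | Next scheduled health-change question |
|---|---|
| Session 1 | Start of Session 2 |
| Session 2 | Start of Session 3 |
| Session 3 | Start of Session 4 |
| Session 4 | Start of Session 5 |
| Session 5 | None listed |

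**Completers**
- All product sessions: 120 × 5 = 600. Without a later question: 120. 120 / 600 = 20%.
- E-cigarette sessions: 120 × 4 = 480. Without a later question: 120. 120 / 480 = 25%.
- By maximum study-product puffs, leaving out the 0 mg/ml practice and flavor sampling: Session 1 is 4 + 20 = 24; each later session is 4 + 4 + 20 = 28; the total is 24 + 4 × 28 = 136. Session 5 share: 28 / 136 = 20.6%.

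**Early withdrawals (assumption)**
The documents give no dropout rate. Suppose d withdrawals in addition to 120 completers, each attending k sessions and then not returning, so that their last session is also uncovered. The share is (120 + d) / (600 + d × k).
- 10% dropout (134 enrolled, d = 14), k = 4: 134 / 656 = 20.4%.
- 20% dropout (150 enrolled, d = 30), k = 2: 150 / 660 = 22.7%.
- 30% dropout (172 enrolled, d = 52), k = 1: 172 / 652 = 26.4%.

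The range is about 20% to 26%. It would be lower if some withdrawals happen at a visit where the questionnaire has already been given.

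**Effect of asking at the call**
Completer coverage goes from 480 / 600 (80%) to 600 / 600 (100%). Withdrawals stay uncovered unless contacted separately, because the call is timed from Session 5.

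**Length of the look-back**
Sessions 2 to 4 are at least 48 hours apart and ideally no more than a week. Against a 7-day interval, the call's look-back is 25 / 7 = 3.6 to 35 / 7 = 5 times as long.

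**The case against.** The strongest case against has four parts.

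1. **Session 5 is not without safety cover.** Sessions are watched throughout, participants are observed for signs of excess nicotine, a post-task CO is taken and CO has adverse-event thresholds, spontaneous reports are accepted, and open events are followed up. All of this stands. A reader might infer that events after the last session are never asked about, or that the session has no adverse-event follow-up. The documents do not support either. The gap is in scheduled questioning about new, delayed events.

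2. **The call may already be covered.** The protocol once refers to the call as a visit and gives it its own data time-point code, so the rule that "adverse events and concomitant medications will be assessed at every study visit" might extend to it. However, that rule is framed as applying while the person is participating and is coupled with vital signs and CO, which a telephone call cannot supply. The call is described as coming after the study has ended. Both accounts of its adverse-event content mention only open forms. This leaves an ambiguity to reconcile and does not fill the gap.

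3. **Other material might ask.** The Adverse Event SOP, the call script and the content of the End of Study Questionnaire are not in the documents. This stands, and it limits the finding to the plan as written.

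4. **No planned inference is damaged.** A reader might infer that final-session counts will be systematically lower, or that about half of participants end on an 18 mg/ml session that goes unmonitored. No per-session summary is planned. The half follows from counterbalancing: each e-liquid condition is last in 6 of the 24 orders, and two of the four conditions are 18 mg/ml (12 / 24). It measures neither harm nor bias. Session 5 occurs in both cigarette groups, and no formal comparison is planned.

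**Conclusion.** The point holds as a limited gap in ascertainment. Followed as written, the plan has no scheduled question about new adverse events after product use in Session 5. For completers this leaves 20% of product sessions and 25% of e-cigarette sessions dependent on what is seen in the lab, the CO reading or what the participant volunteers. With early withdrawals, the share of product sessions is about 20% to 26% under the assumed dropout of 10% to 30%.

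Under-counting of delayed events is expected rather than demonstrated, since the documents give no event rate. The gap affects both cigarette groups and is spread evenly over e-liquid conditions by design. It bears on the completeness of the safety table, not on the primary endpoint or any planned test.

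The conclusion assumes that the SOP, the call script and the End of Study Questionnaire add no such question. If one of them does, the protocol only needs to say so.

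**What to change.** - Add the two existing Health Changes items to the 30-day call, and open an adverse event form for any new event reported.
- Add a column for the call to the Summary of Measures table, with adverse events marked.
- Reconcile the 30 Day Follow-Up Phone Call section with Identifying Adverse Events: state whether the call is a study visit for adverse-event assessment, and align the SOP.
- Ask early withdrawals the same two items at the debrief contact the protocol already plans. Where that contact falls back on mailed information, record that the items could not be asked.
- Record the onset date of each event and report events after Session 5 separately. The 25 to 35 day look-back is longer than the interval between sessions and will collect unrelated events, so pooling would replace one imbalance with another.

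The cost is two questions in a call that already takes place, a longer debrief contact for withdrawals, and changes to protocol, script and table wording. No new visit is needed. If the calls have already been made without these items, the safety report should state the limit on ascertainment after the last session.
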